The purpose of this pilot project is to gather feasibility data to support grant development for a combined alcohol and smoking tele-health mCM intervention that will effectively treat both disorders. The study will be undertaken with the following objectives:

- 1) Develop a multi-component alcohol and smoking tele-health mCM intervention in two successive cohorts of five participants. The first cohort of treatment completers (n = 5) will provide qualitative data from participants and therapists, which will be utilized to modify the treatment components including the therapist manual, mCM apps, and data collection procedures. The second cohort (n = 5) will yield qualitative and quantitative data to refine the intervention and in preparation for a pilot trial.
- 2) Evaluate the feasibility and acceptability (e.g., mCM app reliability, mCM app procedures completion, patient satisfaction) of a tele-health mCM intervention; relative to a comparison group receiving a tele-health intervention without mCM, This will be evaluated in a third cohort that will include a pilot trial randomizing participants to telehealth with mCM (n = 30) or to a comparison group receiving the same phone counseling (Cognitive Behavioral Therapy; CBT) and tele-medicine without mCM (n = 15).

Methods:

Study Design

A successive cohort design will be used to refine the intervention, resulting in three cohorts of participants with AUD and cigarette use. The first two cohorts will focus on treatment refinement, followed by a third cohort participating in a pilot trial.

Successive Cohort Design Stage 1: Feasibility

The successive cohort design (SCD; Epstein et al., 2007) is an iterative process designed to systematically refine and modify behavioral treatments in the early stage of development. The SCD model is a good fit for Stage 1 research, which is designed to generate or modify existing protocols and conduct preliminary testing before initiating larger efficacy trials (Stage II) and effectiveness research (Stage III).

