The first cohort of five participants will complete the tele-health mCM intervention and provide evaluative feedback during an in-depth interview administered at the end of the study, and described in the Measures section below. A coding scheme will be developed for categorizing comments made during the interview based on the study components (e.g., mCM procedures, CBT, interface with smart phone app), subcomponents (e.g., mCM feasibility, CBT burden), and the evaluations drawn (e.g., CBT session too long, video upload still unclear after mCM training).

Successive Cohort Design Stage 2: Treatment Refinement

After the intervention and study have been modified based on information learned from the first cohort, we will treat a second cohort ($n = 5$). Though qualitative data will be evaluated and utilized using methods similar to those of the first cohort, the second cohort will more closely evaluate quantitative data. We will explore relationships of sociodemographic, baseline substance use, and psychiatric comorbidity variables with treatment retention and outcomes. This will identify treatment components to modify or enhance to maximize treatment effectiveness.

Successive Cohort Design Stage 3: Pilot Trial

After treatment modifications from cohort 2, we will conduct a pilot randomized controlled clinical trial. The primary goal of the trial is to evaluate the efficacy of a combined tele-health mCM intervention. The pilot trial will use a two-group design in which 45 participants with an AUD who smoke regularly will be randomized to either:

TELE-HEALTH MOBILE CONTINGENCY MANAGEMENT (mCM) INTERVENTION, a proactive tele-health intervention that combines evidence-based telephone CBT for alcohol and smoking cessation, a tele-medicine clinic for access to nicotine replacement therapy (NRT), and intensive CM therapy administered *via* a smart-phone based application (CM).

OR

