| Iowa Gambling Task | X | | | X | X |
| Balloon Analogue Risk | X | | | X | X |
| Concurrent Treatment Q | X | | | X | X |
| NOSIE | X | | | X | X |
| Medication Adherence | X | | | X | X |
| Qualitative Interview | | | | X | |
| Treatment feasibility measure | | | | X | |
| OUTCOME MEASURES | | | | | |
| Efficacy: Prolonged Abstinence; 7-day; 30-day abstinence | | | X | X | X |
| Quit Attempts | | | X | X | X |
| Tobacco Exposure Questionnaire | | | | X | X |
| Time-line Follow-Back-Quit Attempts | | | | | X |

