Self-reported and bioverified prolonged abstinence from alcohol, smoking, and dual abstinence at the 6-month follow-up will be the primary end-point. Prolonged abstinence will exclude substance use in the first two weeks following the quit date to give participants time to achieve initial abstinence (Hughes et al., 2003). Self-reported prolonged abstinence will be verified by breathalyzer alcohol assessment and assay of cotinine, a metabolite of nicotine in the saliva. Saliva samples will be collected from participants at end of treatment, and at 6-month follow-ups. Deidentified saliva samples will be sent to Salimetrics, and there they will be analyzed for the presence of cotinine using a standard cut point of 10 ng/ml to determine abstinence. A blind sample of 5% will be run again to assure test accuracy of saliva samples. All participants will be asked to provide saliva samples. However if it seems likely that they will have a positive saliva cotinine according to the Tobacco Exposure Questionnaire administered at end of

monitoring at 6-month follow-up, the collected sample may not be sent to Salimetrics for testing.

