Descriptive statistics will be used to summarize all study variables. For continuous variables, means, standard deviations, percentiles, ranges, box plots and histograms will be generated. For categorical variables, frequencies and proportions will be generated. We will construct individual and mean trajectory plots of the longitudinal outcome variables to understand their general trends over time (i.e., post-treatment, 6 weeks and 6 months). Differences in treatment outcomes will be tested via generalized linear modeling. In addition, we will explore the variability and correlation structure of longitudinal variables. We will examine all variables to determine if parametric distributional assumptions (e.g. normality for the continuous variables) are valid. Variables not meeting distributional assumptions will either be transformed or modeled

using nonparametric or semi-parametric methods (e.g. quasi-likelihood methods). In planning a full RCT of the tele-health mCM intervention for AUD and smoking, it is important to evaluate study feasibility and treatment procedures, as well as gain information about effects on proposed outcome variables.

Specific Aim 1: Develop a multi-component alcohol and smoking tele-health mCM intervention.

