We will additionally explore differences in alcohol and smoking abstinence outcomes by treatment. Because the tele-health only intervention is expected to have a uniformly small impact on alcohol and smoking outcomes in comparison to the tele-health mCM intervention, implementation of an imbalanced-samples design, with twice as many participants randomized to the tele-health mCM treatment as to the tele-health only treatment, should maximize power for identifying treatment effects. That said, the proposed sample has 80% power to detect a treatment effect equivalent to Cohen's $d = 0.76$. For reference, in our pilot study of 22 smokers with PTSD, tele-health mCM yielded an effect size of Cohen's $d = 0.79$ at the 3-month follow-up. In particular, comparisons by treatment at post-intervention, 6 week follow-up, and 6-month follow-up will be made regarding alcohol consumption (drinks/week, number of heavy drinking episodes, proportion of days abstinent, and achieving recommended drinking limits) and smoking (number of cigarettes smoked each day and number of days of smoking abstinence) *via*

generalized linear modeling, which can accommodate normally and non-normally distributed (e.g., count) variables.

References

- Acuff, S. F., & Murphy, J. G. (2017). Further examination of the temporal stability of alcohol demand. *Behavioural Processes, 141*, 33-41. doi:10.1016/j.beproc.2017.03.020.
- Alessi, S. M., & Petry, N. M. (2013). A randomized study of cellphone technology to reinforce alcohol abstinence in the natural environment. *Addiction, 108*(5), 900-909. doi:10.1111/add.12093
- drinking outcomes in clinical trials. *Journal of Studies on Alcohol, 61*, 55-63.
- Bechara. A., Damasio, A.R., Damasio, H., Anderson, S.W. (1994). Insensitivity to future consequences following damage to human prefrontal cortex. *Cognition, 50*, 7-15.

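### Six-month abstinence is both the primary efficacy end-point and an added exploratory outcome, and no rule says which of the three abstinence outcomes defines success

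*Combined protocol and SAP*

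**What the plan says.** The combined protocol and SAP describes the purpose of the randomised cohort in two ways.

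**As a feasibility pilot.** The Objectives section opens with "The purpose of this pilot project is to gather feasibility data to support grant development". Objective 2, which the randomised cohort serves, is to "Evaluate the feasibility and acceptability (e.g., mCM app reliability, mCM app procedures completion, patient satisfaction) of a tele-health mCM intervention". The Stage 1 paragraph places this kind of work before larger (Stage II) efficacy trials. Under Specific Aim 2 in Data Analyses, abstinence enters as an extra: "We will additionally explore differences in alcohol and smoking abstinence outcomes by treatment".

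**As an efficacy trial.** The section on Stage 3 (Pilot Trial) states: "The primary goal of the trial is to evaluate the efficacy of a combined tele-health mCM intervention". The section on outcome measurement and biochemical verification states: "Self-reported and bioverified prolonged abstinence from alcohol, smoking, and dual abstinence at the 6-month follow-up will be the primary end-point". Table 2 labels its abstinence row "Efficacy: Prolonged Abstinence; 7-day; 30-day abstinence". The Aim 2 text justifies the 2:1 allocation by power to find treatment effects and claims 80% power at Cohen's d = 0.76.

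On method, the plan says "Differences in treatment outcomes will be tested via generalized linear modeling" and then that "comparisons by treatment at post-intervention, 6 week follow-up, and 6-month follow-up will be made regarding alcohol consumption" and smoking. The named outcomes are drinks per week, heavy drinking episodes, proportion of days abstinent, meeting drinking limits, cigarettes per day and days of smoking abstinence.

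**The concern.** A primary end-point tells the reader beforehand which result will answer the trial's question. Here three outcomes share that label, the text does not choose among them, and another section treats the whole family as exploratory. A later report could quote either set of sentences and stay faithful to the protocol.

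The pilot exists to support a grant for a larger trial. If the outcome to stress is picked once results are known, a favourable single outcome could be read as primary evidence of efficacy, or a null as evidence of no effect, and either could carry into the design of the next study.

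**Working it through.** **1. The sections side by side**

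| Place | Status given to abstinence |
|---|---|
| Objectives; Objective 2 | Not an objective; feasibility and acceptability are |
| Stage 3: Pilot Trial | Efficacy is the primary goal |
| Outcome Measurement | Three prolonged-abstinence outcomes form the primary end-point |
| Data Analyses, Aim 2 | Additionally explored; prolonged and dual abstinence absent from the listed comparisons |

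The Data Analyses section gives no alpha, sidedness, hierarchy, success rule or multiplicity rule. The singular noun in the end-point sentence leaves three readings open: dual only, all three, or any one.

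**2. The plan's own figure**

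The stated power is 80% at d = 0.76, with no end-point or alpha named. With 30 versus 15, the noncentrality is 0.76 x sqrt(30 x 15 / 45) = 0.76 x 3.162 = 2.403.

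- Two-sided 0.05: Phi(2.403 - 1.960) = 67.1% (65.2% with the t distribution).
- One-sided 0.05: Phi(2.403 - 1.645) = 77.6% (76.4% with t).

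The 80% does not reproduce for the randomised comparison. That is a separate matter and the contradiction does not depend on it. It matters here because a standardised mean difference with no named outcome does not show which end-point the trial was sized for.

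**3. What each reading would imply under no effect**

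The documents give no abstinence rates, so these are assumed. The three scenarios for (smoking, alcohol, dual) are (15%, 20%, 8%), (25%, 30%, 15%) and (30%, 30%, 20%). Each participant falls in one of four cells: both = d, smoking only = s - d, alcohol only = a - d, neither = 1 - s - a + d. For the first scenario these are 0.08, 0.07, 0.12 and 0.73. The same cells were used in both arms, with 30 and 15 participants, at least 200,000 replicates and nominal two-sided 0.05. Wald tests with a zero cell were counted as non-significant.

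| Test | Any one of three | Dual alone | All three |
|---|---|---|---|
| Fisher exact | 6.3-7.5% | 1.7-3.1% | below 1% |
| Wald, logistic model | 4.2-7.2% | 0.7-2.2% | below 1% |
| Likelihood ratio, logistic model | 12.6-15.8% | 6.1-7.0% | below 1% |

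The plan says only that generalized linear modelling will be used, so the Wald and likelihood-ratio rows are both compatible with it. Part of the likelihood-ratio figure is that test's own small-sample size, since a single test of dual abstinence already exceeds 5%. The textbook value for three independent tests, 1 - 0.95^3 = 14.3%, does not apply, because dual abstinence is nested in the other two outcomes.

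**4. What 30 versus 15 can show**

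For an illustrative 30% versus 10%, the half-width is 1.96 x sqrt(0.3 x 0.7 / 30 + 0.1 x 0.9 / 15) = 1.96 x sqrt(0.007 + 0.006) = 1.96 x 0.114 = 0.22. The interval is 20 +/- 22 points, or about -2 to 42. This is a large-sample approximation and is rough with 15 in one arm.

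**The case against.** The strongest reply is that the document as a whole is plainly a pilot. It calls itself Stage 1 work, leaves efficacy to later trials, frames the analysis as preparation for a full randomised trial, and describes abstinence differences as explored. On that view the efficacy sentence is one loose line under a heading that says pilot, and unadjusted exploratory comparisons need no multiplicity rule. For a trial consistently labelled exploratory, this would be right, and it limits the harm. It does not remove the contradiction, because the primary-goal and primary-end-point sentences are current text and say the opposite.

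A reader might go further and infer that the plan declares success if any one of three p-values falls below 0.05, so that false-positive risk is inflated to 13-16%. The documents do not support that. No section states such a rule or an alpha, and the all-three and dual-only readings are just as open. Even under the any-one reading, Wald and Fisher tests give only about 4-8%. The listed comparisons do not specify a test of prolonged or dual abstinence at all. Nor does any passage commit the sponsor to reporting a positive or a null efficacy conclusion.

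It is also fair to say that, once no efficacy claim is made, choosing one main abstinence outcome is partly a matter of judgement.

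**Conclusion.** Wrong as written, as an internal contradiction of low-to-moderate severity. The protocol gives 6-month abstinence two incompatible statuses and leaves success undefined across three outcomes, so the choice can be made after the data are seen. That conclusion rests on the text alone.

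The numerical consequence is secondary: from below 1% to about 16% under no effect, depending on the reading and the test, at abstinence rates that are assumptions. An interval of roughly -2 to 42 points for a 20-point difference shows that this sample could not settle efficacy in either direction.

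**What to change.** Change the wording in three places.

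- **Stage 3: Pilot Trial.** Replace the efficacy goal with the feasibility and acceptability goal of Objective 2.
- **Outcome Measurement and Biochemical Verification.** Name prolonged dual abstinence at 6 months as the single main abstinence outcome, with alcohol-only and smoking-only prolonged abstinence as secondary. The title's concurrent abstinence supports this choice.
- **Data Analyses, Specific Aim 2.** Add prolonged and dual abstinence to the listed comparisons. State that all abstinence differences are reported as estimates with 95% confidence intervals and no efficacy claim. Bring the power statement and the allocation rationale into line with that status.

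No alpha split is then needed, and the change adds no participants, visits or assays. The cost is that dual abstinence is the rarest of the three: it will have the fewest events, and a relative effect such as an odds ratio will be the least precisely estimated. That matters less once the result is an estimate for planning and not a test.

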For each video recording, participants will be asked to 1) begin a recording using the smartphone device; 2) show the pre-assessment zero breathalyzer reading to the camera; 3) expel air from lungs into the breathalyzer while being video-recorded; 4) show the final reading to the camera; and 5) log in to a secure website through the app interface on the Google Android operating system that includes pages tailored to each participant, and upload the video recordings using encrypted network connections. Immediately after completing a breathalyzer reading, participants will provide a CO reading following the same procedures. Participants will receive a chart with descriptions detailing the rules for earning incentives. Because reinforcers are most effective when delivered immediately after the target behavior is performed (Lattal, 2010), the phone app is designed to allow therapists to provide quick feedback on abstinence status, financial amount earned, and how the amount was calculated. Participants will be informed that results are pending video review from the study coordinator to confirm validity. Based on a previously published protocol using mobile CM for alcohol, the alcohol assessments for our study will occur from awakening until the participant goes to sleep at night, with a higher probability of assessment occurring during high-risk alcohol consumption times during the day (Alessi & Petry, 2013). High-risk consumption times will be based on alcohol consumption patterns, rather than smoking patterns, because alcohol is eliminated from body more quickly than CO from smoking. The alarm algorithm targets a mean of 10 readings each week, with a variable number of alarms across weeks. This will ensure that there are no times in which participants are aware that there will be no more assessments for the week. The app is designed to alarm-prompt assessments that could potentially occur at any point during

waking hours, occurring on at least five high-risk periods each week, and twice in the same evening on at least two evenings each week. This procedure is designed to ensure that participants do not know when they will have a long period of time between readings that would provide an opportunity for drinking alcohol that would be metabolized before the next reading. When prompted, participants will have one hour to submit their reading, with reminder prompt at 30 minutes. Similar procedures have been employed with good adherence and have been well-tolerated in one published study (Alessi & Petry, 2013). Participants will be allowed to opt out of alarms for one hour if there are circumstances that would prevent them from safely or conveniently responding to an alarm (e.g., while driving, at a meeting, etc.). When participants are alarm-prompted to submit an alcohol reading, they will also receive a text message sent to their personal phone number informing them that they have an alcohol reading due for submission. The text message will read "A research alarm has gone off. Please upload a video by xxxx!" Nothing in the text message to participants will give away the nature of this study. This text message is designed to assist participants who are in loud areas or will not be near enough to the study-provided phone to hear the prompt. This additional informational procedure is based on qualitative feedback from participants in our first two cohorts, who wanted to adhere to monitoring but did not always hear the study phone prompts. Participants who prefer not to receive text messages on their personal phones will be able to opt out of text messages from the study at any time.

Because CO from smoking a cigarette is metabolized more slowly than a drink of alcohol, CO can be assessed less frequently. To take advantage of this feature of CO, and to reduce participant burden, we will ask participants to provide CO assessment videos at two times each day chosen by the participant, as long as the two CO assessments for that day are at least 8 hours apart. By designing the protocol to have CO assessments at times chosen by the participant, we expect to relieve participants of the burden to carry both the alcohol breathalyzer and the CO monitor during the day. This way, only the breathalyzer must be kept with the participant to respond to alarms. For example, participants could choose to complete the CO assessments before leaving the house in the morning and after returning in the evening. Participants will submit videos as needed before the practice week as study staff coordinate approvals for smoking cessation pharmacotherapy with the participants' medical provider. Once the study practice week is initiated, participants will be compensated for practicing this data collection for one week (see contingency table in mCM manual). Through the smart-phone app, participants log-in to a secure website to upload their video recordings and see personalized information regarding their reinforcement information. Study coordinators can monitor validity and compliance on a daily basis and offer feedback to ongoing participants regarding compensation so they are well-practiced at the procedures by the time contingent reinforcement is initiated. During the practice week, participants will be compensated \$2.00 for completing a valid alcohol reading, and \$1.00 for a valid smoking reading. After the practice week, the MM group will receive \$3 for providing a valid on-time Breathalyzer reading and \$1.00 for providing a valid on-time CO reading, regardless of whether they are abstinent from the substance. After the

practice week, monetary reinforcement for the mCM group becomes contingent on abstinence, operationally defined as breathalyzer readings that are < 0.02 BrAC and CO readings that are < 6 ppm (after the first week). In the first week of abstinence, smoking cessation compensation will be based not on CO < 6ppm, but on a proportion of participant's baseline CO as defined by Lamb (Lamb, Morral, Kirby, Iguchi, & Galbicka, 2004). Because an escalating, versus a fixed reinforcement schedule has produced higher abstinence rates (Heil et al., 2008; Stoops et al., 2009), an escalating schedule will be used in this protocol. If on each day, if a participant submits all required videos, and all videos suggest that they have been abstinent from both alcohol and cigarettes, they will receive a \$5 bonus (Sunday through Wednesday) or a \$10 bonus (Thursday through Saturday). Participants will be asked to return the monitoring equipment at the end of the monitoring period. To ensure that participants return the breathalyzer, CO monitor, and phone, we are providing postage paid return mailers and adding a \$35 incentive for equipment return.

Cognitive Behavioral Therapy for Alcohol Use Disorder and Smoking Cessation

Tele-health mCM treatment will include 4 sessions of CBT telephone counseling for alcohol and smoking cessation, outlined for the therapists in the treatment manual. Though CBT has not been combined with CM in previous AUD treatment, CBT has been used in combination to concurrently treat alcohol use and smoking, and it was feasibly implemented and well-tolerated (Laaksonen, Vuoristo-Myllys, Koski-Jannes, & Alho, 2013). We have developed the CBT manual by drawing on the cognitive-behavioral coping skills therapy portions of the treatment manual generated from Project MATCH (NIAAA coping skills manual from Project MATCH, 2003) and the Integrated Care for Smoking Cessation manual (McFall et al., 2010), two treatment with empirical evidence of efficacy (R. Kadden, Carbonar, Litt, Tonigan, & Zweben, 1998). Due to the substantial overlap in treatment procedures and skills acquired in CBT for alcohol and smoking, the first 40 minutes of each session will be devoted to material that applies to both problems. The final 20 minutes of each session will primarily be devoted to CBT for alcohol, as the CBT for alcohol from which our manuals were developed has more total treatment time than the manual from which CBT for smoking was adapted.

Pharmacotherapy for Smoking Cessation

Treatment will include standard pharmacotherapy for smoking cessation. This consists of bupropion, nicotine patch, and an 8-week course of < 2 rescue methods (e.g., nicotine gum, lozenge) in participants for whom these medications are not contraindicated or who receive medical clearance from a physician. Participants will be screened for suitability for NRT or other smoking cessation medication. Participants who report being contraindicated to bupropion or NRT (i.e. high blood pressure not controlled by medication) must obtain authorization from their physician prior to receiving the corresponding medication. If the patient does not have a physician, or the physician does not respond to information requests, [name] will make determinations about whether to authorize study medications. [name] will prescribe a tailored amount and delivery type of NRT based on number of cigarettes smoked per

day, quit history, medical conditions, and psychiatric comorbidities. NRT and bupropion will be provided *via* mail. [name] will write the NRT and/or bupropion prescriptions and work with other study staff and participants' primary care physician to discuss contraindications. Eligible participants will be provided bupropion for eight weeks. Participants will be informed that they can discuss whether or not to continue bupropion use for relapse prevention with their personal physician. At the end of the study's course of bupropion, participants will be reminded to confer with their physician re: continued bupropion use. For participants who relapse to smoking or are unable to quit, [name] will make decisions about whether to prescribe additional NRT to assist the participant in their continued attempts to stop smoking.

6-Month Follow-Up

All participants will be asked to provide a saliva sample to bioverify smoking abstinence. Alcohol abstinence will be measured by self-report, breathalyzer, and a blood spot sample that measures PEth at the 6-month follow-up. Participants will be encouraged to attend the 6-month follow-up assessment in the lab. However, if participants are unable due to transportation issues or decline to attend the 6-month follow-up, we will administer interview and questionnaire measures by phone and collect saliva samples by mail.

Drinking and smoking will also be monitored by the smart phone app with entries during the day for any drinking and smoking occasions. In addition, before the participants' set bedtime, they will be prompted to estimate their total amount of drinking and smoking during the day. Finally, at the 6-month follow-up, participants will complete a timeline follow-back assessment of alcohol use and smoking, conducted by phone. At the screening session, we will administer a questionnaire developed specifically for this study that asks about beliefs regarding concurrent treatment of substance use disorders. This is called the Concurrent Treatment Questionnaire in Table 2. This will be administered at the screening session, end of monitoring, and 6 month follow up. The NOSIE, Nicotine and Other Substance Interaction Expectancies Questionnaire, will also be administered at these points (Rohsenow, et al. 2005).

Table 2: Study Baseline and Outcome Measures

| | BL | CBT | PT | EM | FUP |
|-----------------------------|----|-----|----|----|-----|
| BACKGROUND VARIABLES | | | | | |
| Demographics | X | | | | |
| AUDIT | X | | X | X | X |
| RAPI | X | | X | X | X |
| Sheehan Disability Scale | X | | | | X |
| FTND | X | | X | X | X |
| SCID | X | | | | |
| CIWA | X | | | | |
| QSU | X | | X | X | X |
| MNWS | X | | | | |
| Smoking History measure | X | | | | |
| PANAS | X | | X | X | X |

| | | | | | |
|--|---|---|---|---|---|
| AASES | X | X | | X | X |
| RSEQ | X | | X | X | |
| ISI | X | | X | X | X |
| MTSS | X | X | X | X | X |
| NRT Contraindications | X | | | | |
| DAR | X | | X | X | X |
| Patient Health Q-9 | X | | | X | X |
| Alcohol Readiness to Change | X | | X | X | X |
| Delay Discounting task | X | | X | X | X |
| Cigarette Purchase Task | X | | | X | X |
| Alcohol Purchase Task | X | | | X | X |
| Self-efficacy for Smoking | X | X | X | X | |
| NSSI checklist | X | | | X | X |
| Fidelity ratings | | X | | | |
| Penn Alcohol Craving Questionnaire | X | X | X | X | X |
| ITASr-SF | | | X | | |
| Positive and Negative Expectancies | X | X | X | X | X |
| Smoking Consequences Questionnaire | X | X | X | X | X |
| Anxiety Sensitivity Index-Revised 36 | X | | | X | X |
| OSS | X | | | X | X |
| Voils Medical Adherence | | | | X | |
| Timeline Follow Back | | | | | X |
| PROCESS MEASURES | | | | | |
| Smoking cessation aids | | | X | X | X |
| Conners' ADHD Scale | X | | | X | X |
| Barratt Impulsivity Scale | X | | | X | X |
| Conners CPT | X | | | X | X |
| Iowa Gambling Task | X | | | X | X |
| Balloon Analogue Risk | X | | | X | X |
| Concurrent Treatment Q | X | | | X | X |
| NOSIE | X | | | X | X |
| Medication Adherence | X | | | X | X |
| Qualitative Interview | | | | X | |
| Treatment feasibility measure | | | | X | |
| OUTCOME MEASURES | | | | | |
| Efficacy: Prolonged Abstinence; 7-day; 30-day abstinence | | | X | X | X |
| Quit Attempts | | | X | X | X |
| Tobacco Exposure Questionnaire | | | | X | X |
| Time-line Follow-Back-Quit Attempts | | | | | X |

